9. RESEARCH METHODS

9.1. Study design

This is a multicenter, single-arm, retrospective observational study to describe the safety, treatment patterns and effectiveness of nirmatrelvir/ritonavir among patients with COVID-19 in China. Approximately 5 hospitals and 1000 patients are planned to be included in this study. Retrospective data abstraction will start after site ethics committee approval. Patients who initiated nirmatrelvir/ritonavir treatment between 11 February 2022 and 31 August 2022 will be included in this study. Continuous recruitment of patients in each site will be employed. For analyzing purpose, the index date for an individual patient is defined as the date of initiating nirmatrelvir/ritonavir treatment. The baseline period for an individual patient is defined as the period from the first day of hospitalization through the index date to capture the patient's baseline clinical characteristics, medical history, and comorbidity. The observation period for an individual patient is defined as the period from initiation of nirmatrelvir/ritonavir (i.e., index date) until discharge from hospital, death, or a maximum of 28 days after the last dose of nirmatrelvir/ritonavir, whichever comes first. The study data cut-off date will be 02 October 2022. Each patient will be included in the study only once. If the patient initiated nirmatrelvir/ritonavir treatment more than once between 11 February 2022 and 31 August 2022, only the first treatment course will be included for analysis. The study design schematic is presented in [Figure 1](#).

Figure 1. Study design schematic

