9.3.7. Time to alleviation of all targeted COVID-19 signs and symptoms

The targeted signs and symptoms of COVID-19 (described in section 9.3.3) will be used for the analysis of time to alleviation calculation. For a patient, the targeted signs and symptoms recorded in either baseline or observation period will be evaluated.

The First Alleviation Date for a targeted sign/symptom is the date when alleviation is firstly recorded in medical records during the observation period

Event Date = The last date of (The First Alleviation Dates for ALL targeted signs/symptoms to be evaluated)

The time to alleviation of all targeted COVID-19 signs and symptoms is defined as:

- For a patient with the Event Date, it will be calculated as (Event Date) – (Index Date) +1.
- For a patient without the Event Date, it will be calculated as (End of Observation Date) – (Index Date) +1 and be considered as a censoring time. ^{7 12}

9.3.8. Time to two consecutive negative SARS-CoV-2 test results / CT ≥ 35

For patients with at least two SARS-CoV-2 tests (specimens collected in two different calendar days) after treatment initiation during observation period, the first day of a negative SARS-CoV-2 test / CT ≥ 35 from two consecutive negative results is considered as an Event Date.

The time to event of two consecutive negative SARS-CoV-2 test results / CT ≥ 35 in this study is defined as:

- For a patient with the Event Date, it will be calculated using (Event Date) – (Index Date) +1.
- For a patient without the Event Date, it will be calculated as (End of Observation Date) – (Index date) + 1 and be considered as a censoring time.

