9.7.1. Analysis sets

- Full Analysis Set (FAS):

The FAS will include all patients who meet the inclusion criteria and do not meet the exclusion criteria described in section 9.2.

- Safety Analysis Set (SAS):

The SAS will include all patients from FAS.

- Effectiveness Analysis Set 1 (EAS1):

The EAS1 will include all patients from FAS who had at least one of the effectiveness variables collected and had the latest positive SARS-CoV-2 test result within 5 days prior to administration initiation.

- Effectiveness Analysis Set (EAS):

The EAS is a subset of EAS1 and will include patients who had mild or moderate COVID-19 illness at baseline and had at least one risk factor (defined in section 9.3.1) for progression to severe COVID-19 at baseline.

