9.7.3.2. Analysis of effectiveness endpoints

The analyses of effectiveness endpoints will be based on EAS1 and EAS, and the following will be presented:

Proportion of patients with COVID-19 disease severity (described in section 9.3.2) progressed or death from any cause and corresponding 95% CI will be summarized.

Time to alleviation of all targeted COVID-19 signs and symptoms (described in section 9.3.7) will be summarized by K-M plots with the median time and corresponding 95% CI.

Number and percentage of patients with two consecutive negative SARS-CoV-2 test results / CT \geq 35 (specimens collected in two different calendar days) and corresponding 95% CI will be summarized for the patients with at least two SARS-CoV-2 tests after treatment initiation.

Time to the first negative SARS-CoV-2 test result / CT \geq 35 from two consecutive negative SARS-CoV-2 test results / CT \geq 35 (specimens collected in two different calendar days) among patients with at least two SARS-CoV-2 tests (described in section 9.3.8) will be summarized and plotted in a K-M curve with the median time and corresponding 95% CI.

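### Both Kaplan-Meier endpoints censor at the end of observation, so deaths count as patients who could still clear or recover and unassessed days count as event-free; the two biases oppose and their net is unknown

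*Protocol*

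**What the plan says.** Section 9.3.7 (alleviation) gives the rule for patients without the event: "For a patient without the Event Date, it will be calculated as (End of Observation Date"), less the index date, plus one, taken as a censoring time. Section 9.3.8 (viral clearance) repeats it. Neither section refers to the date of the last test or the last symptom record.

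Under section 9.1, observation starts on the index date and lasts "until discharge from hospital, death, or a maximum of 28 days after the last dose of nirmatrelvir/ritonavir, whichever comes first". Death is therefore one of the dates on which a patient is censored.

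Section 9.7.3.2 says that alleviation "will be summarized by K-M plots with the median time and corresponding 95% CI", and it plans a Kaplan-Meier curve and median for clearance as well. It names no competing-risk method.

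Section 9.7.1 admits to EAS1 any FAS patient with some effectiveness data and a recent positive test. This puts no limit on baseline severity. EAS is the subset with mild or moderate illness and at least one risk factor.

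**The concern.** Kaplan-Meier assumes that a censored patient has the same future chance of the event as those still followed, and that the patient was known to be event-free up to the censoring time. The plan's rule breaks both assumptions.

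- **Death.** A patient who has died can no longer clear the virus or recover. Censoring at death gives that patient the future of the survivors, so the curve rises too high.
- **Unassessed time.** The data come from routine hospital records and the protocol sets no test or symptom-charting schedule. If the last test was on day 6 and discharge on day 20, the rule counts 14 untested days as known event-free. That holds the curve too low. For clearance the unobservable stretch is longer still, because the final test cannot start a pair of negatives.

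At stake are two of the four effectiveness endpoints: the plotted curves, the medians and their confidence intervals. Under the planning assumption in section 9.5 that 20% of patients reach two consecutive negatives, 80% would carry a censoring date, so the choice of date is not a detail.

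**Working it through.** The protocol states no figure for either endpoint, so there is none to reproduce. The size was explored by simulation. **Every input below is an assumption.**

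**Inputs.** Clearance time is Weibull with shape 1.5 and scale 11.5 days, rounded up to whole days, so the probability of clearance by day t is 1 − exp(−(t/11.5)^1.5).
- Median before rounding: 11.5 × (ln 2)^(2/3) = 9.0 days.
- Day 14: 1 − exp(−1.343) = 73.9%.
- Day 28: 1 − exp(−3.799) = 97.8%.

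The 50% point falls almost exactly on day 9, so a move from 9 to 10 days can reflect a very small change in the curve.

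**Estimators.** Kaplan-Meier is 1 − Π(1 − d/n), with d events among n at risk on each day. With death competing, cumulative incidence is the sum over days of S × d/n, where S is the probability of being alive and event-free just before that day.

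**1. Death as censoring.** A share of patients is assigned a death day, uniform on days 3 to 14. Those who have not cleared by then die uncleared.

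| Assigned to die | Die uncleared | Kaplan-Meier, day 28 | Deaths kept as non-events, day 28 | Excess |
|---|---|---|---|---|
| 1% | 0.5% | 97.8% | 97.3% | 0.5 points |
| 5% | 2.7% | 97.8% | 95.2% | 2.6 points |
| 10% | 5.4% | 97.8% | 92.6% | 5.2 points |

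The excess is close to the share dying uncleared. The median reads 9 days under the plan's rule and 10 with deaths kept, which is the near-tie noted above. If instead 5% of patients die and none of them clears, Kaplan-Meier gives 97.7% against 92.9%, an excess of 4.8 points. A second model (gamma clearance with mean 7 days, tests every 1 or 2 days) gave the same pattern with the median unchanged.

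**2. Censoring after the last assessment.** Here there are no deaths, the last informative test is uniform on days 4 to 20, and the gap from that test to the end of observation is uniform with the mean shown. The pair rule is not modelled separately.

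| Mean gap | Plan's rule: median | Plan's rule: day 14 | Last-test censoring: median | Last-test censoring: day 14 |
|---|---|---|---|---|
| 0 days | 9 | 74% | 9 | 74% |
| 1 day | 10 | 71% | 9 | 74% |
| 3.5 days | 10 | 64.5% | 9 | 74% |
| 7 days | 11 | 60.5% | 9 | 74% |

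The largest shift is 73.9 − 60.5 = 13.4 points and two days. It is this large because about 39% of patients are still uncleared at their last test. With the last test on days 10 to 28 and a 3.5-day mean gap, the plan's rule gives 9 days and about 72%. With tests every 1 or 2 days in the gamma model, the shift is 0 to 0.8 points.

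**The case against.** These are secondary endpoints in a single-arm descriptive study whose primary objective is safety. The protocol reports plots and medians rather than a day-28 probability, and deaths hardly move the median. Deaths are not hidden, because a separate endpoint reports the "Proportion of patients with COVID-19 disease severity (described in section 9.3.2) progressed or death from any cause". EAS is limited to mild or moderate illness, where deaths should be few. With frequent testing the second bias is negligible. Section 9.7 also lets the SAP modify the plan.

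Most of this stands, and it limits the weight of the point. It does not remove it. The separate death endpoint does not correct the plotted curve, EAS1 can include severe and critical patients, and the protocol itself fixes the censoring date rather than leaving it open.

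Three stronger readings are tempting, and the documents do not support them.

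- **That the two-test condition biases both curves.** Section 9.3.8 applies it only to clearance: "For patients with at least two SARS-CoV-2 tests (specimens collected in two different calendar days) after treatment initiation during observation period". For alleviation, section 9.3.7 says only that "the targeted signs and symptoms recorded in either baseline or observation period will be evaluated". The condition is also stated openly in the endpoint, since the clearance proportion "will be summarized for the patients with at least two SARS-CoV-2 tests after treatment initiation". One can construct 45/90 = 50% reported against 45/100 = 45%, but that supposes that 10% lack two tests and that none of them cleared. Counting untested patients as failures is itself debatable. In the gamma model, with early discharge unrelated to clearance, restoring these patients moved the Kaplan-Meier curve by at most about 0.2 points.
- **That the results will look too favourable.** The death bias raises the curve and the assessment-gap bias lowers it.
- **That the median is wrong by a definite amount.** The shift runs from nothing to two days, depending on a gap that the protocol does not give.

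**Conclusion.** The point holds as a flaw in a stated rule, with two opposing effects. Censoring deaths overstates late clearance and alleviation by about the share dying without the event: 0.5 to 5 points at day 28 for 0.5% to 5.5%, with at most about one day in the median. The effect is likely larger in EAS1 than in EAS. Censoring after the last assessment understates the curve by 0 to 13 points at day 14 and lengthens the median by 0 to 2 days.

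These ranges depend on the assumed clearance curve, death shares, last-test days and gaps. The documents supply none of them for this population, so neither the net direction nor the net size can be stated. The two-test condition is a declared restriction of the clearance endpoints and is not part of this finding.

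**What to change.** In sections 9.3.7 and 9.3.8, censor surviving patients without the event at the last date on which the event could have been observed. For alleviation that is the last symptom record; for clearance, the last test that could start a two-negative pair.

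In section 9.7.3.2, treat death as a competing event and report cumulative incidence. A simpler route is to keep deaths event-free to the maximum follow-up, which gives the same curve when there is little other censoring.

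For the clearance endpoints, report how many patients were excluded for having fewer than two tests and why (death, discharge). At most, add an all-patient denominator as a sensitivity analysis.

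The cost is small. Table 1 already calls for test, symptom, death and discharge dates, so the change needs new wording and slightly more analysis. The late clearance figure will be slightly lower once deaths are kept as non-events. Neither change deals with discharge that depends on recovery, which the documents do not allow to be sized.

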9.4. Data sources

Individual-level data will be retrospectively abstracted from the HIS and LIS to the eCRF from all sites participating in the study. The source of collected data will be all elements that can constitute a reliable in the patients' medical record (e.g., consultation notes, discharge summaries, laboratory test results, recorded prescription data, imaging data, and any other documentation of communication with other health care providers). Variables and data abstracted from source documents included are described in section 9.3, and will be collected by the delegated trained site personnel and entered directly into the web-based eCRFs. No personal identification information will be abstracted. Only de-identified data will be used in analysis.

9.5. Study size

There is no formal hypothesis testing for this study. This study is planned to include approximately 1000 individuals who initiated nirmatrelvir/ritonavir between 11 February 2022 and 31 August 2022. The primary objective of the study is to describe real-world safety of nirmatrelvir/ritonavir, and one of the primary safety endpoint is the proportion of patients experiencing AEs with explicit attribution to nirmatrelvir/ritonavir.

With a sample size of 1000, there will be a probability of >99.9% to observe an AE related to nirmatrelvir/ritonavir with a low incidence rate of 1% in at least one patient, and a probability of 95.0% to observe an AE related to nirmatrelvir/ritonavir with an even lower incidence rate of 0.3%²⁹ in at least one patient.

Table 4. Probabilities to observe an AE of different incidence rates

	Incidence rates		
Sample Size	1%	0.5%	0.3%
1000	> 99.9%	99.3%	95.0%

Note: The sample size and power is calculated based on the exact probabilities of the Binomial distribution, the probability of observing at least one event in n observations = $1 - (1-p)^n$.

For the effectiveness endpoint of proportion of patients with two consecutive negative SARS-CoV-2 test results, assuming that 20%³⁰ of patients will have negative SARS-CoV-2 test results from two consecutive respiratory specimens collected in two different calendar days, and 80% and 50% patients will be evaluable with at least one of the effectiveness endpoints data collected and in addition having at least one risk factor, samples of 800 and 500 individuals will provide a 95% CI with a half width of 2.77% and 3.50%, respectively.

Table 5. Precision for evaluating effectiveness for different numbers of evaluable patients

Scenarios	Evaluable patients	Half width of CI *
Included patients who had mild or moderate COVID-19 illness and had at least one risk factor at baseline for progression to severe COVID-19	500	3.50%
Included patients who had at least one of the effectiveness variables collected.	800	2.77%

*Note: The half width confidence interval is calculated according to the formula $z * \sqrt{p * (1 - p) / n}$, where $z = 1.96$ for a confidence level (α) of 95%, p = proportion, n = #of evaluable patients.

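### Table 5 states the precision of the viral-clearance proportion on a wider denominator than the endpoint uses, so 2.77% and 3.50% are best-case half-widths at a 20% rate

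*Protocol*

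**What the plan says.** Section 9.5 starts from about 1000 patients and sizes the clearance proportion on the assumption that 20% "of patients will have negative SARS-CoV-2 test results from two consecutive respiratory specimens collected in two different calendar days". It gets to its two sample sizes through a further assumption on available data, the last part of which concerns baseline risk factors: "80% and 50% patients will be evaluable with at least one of the effectiveness endpoints data collected and in addition having at least one risk". From these it concludes that "samples of 800 and 500 individuals will provide a 95% CI with a half width of 2.77% and 3.50%, respectively". Table 5 repeats the figures. Its 800 row is labelled "Included patients who had at least one of the effectiveness variables collected", and its 500 row is labelled by mild or moderate illness plus at least one baseline risk factor. The note under the table gives the simple normal-approximation half-width with z = 1.96.

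The endpoint itself is narrower. Section 9.1.2 defines it only among patients with at least two tests after initiation. Section 9.7.3.2 says that the number, percentage and interval "will be summarized for the patients with at least two SARS-CoV-2 tests after treatment initiation", within EAS1 and EAS. Section 9.7.1 admits to EAS1 only patients who, besides having an effectiveness variable, "had the latest positive SARS-CoV-2 test result within 5 days prior to administration initiation". The EAS is a subset of EAS1, so it inherits that condition.

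**The concern.** A half-width is only as good as its n. Here n counts patients who have any effectiveness information at all, while the endpoint counts patients with a specific kind of information. The first condition is much weaker: a record of severity progression or death is an effectiveness variable under Section 9.1.2, and a patient can have one without a single test after starting treatment. The 5-day condition on the last positive test is a second filter that Section 9.5 does not mention.

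At a fixed rate, a smaller n can only widen the interval. This is the protocol's only precision statement for effectiveness, and it is worded as what the samples will deliver. A reader could therefore expect a tighter interval for viral clearance than the analysis may produce.

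**Working it through.** **Inputs from Section 9.5:** total about 1000; evaluable shares 80% and 50%; p = 20%; z = 1.96; half-width = z × √(p(1 − p)/n).

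**Step 1: reproduce the stated figures.**
- 0.80 × 1000 = 800: 1.96 × √(0.20 × 0.80/800) = 2.772%. Stated: 2.77%.
- 0.50 × 1000 = 500: 1.96 × √(0.20 × 0.80/500) = 3.506%. Stated: 3.50%; correctly rounded this is 3.51%.

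The arithmetic follows from the inputs, apart from the last digit of the second figure. A Wilson interval at n = 500 would give 3.500%, but that is not the formula printed under Table 5.

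**Step 2: compare the denominators.**

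| Condition | Section 9.5 / Table 5 | Endpoint as analysed |
|---|---|---|
| At least one effectiveness variable | yes | yes |
| Mild or moderate illness and a risk factor | 500 row only | EAS only |
| Latest positive test within 5 days before initiation | not named | EAS1 and EAS (9.7.1) |
| At least two tests after initiation | not named | yes (9.1.2, 9.7.3.2) |

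**Step 3: apply the formula to the endpoint's denominator.** Let s be the share of the 800 (or 500) who meet both unnamed conditions. The protocol gives no value for s, so the values below are assumptions. p stays at 20%.

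| s | n from 800 | Half-width | n from 500 | Half-width |
|---|---|---|---|---|
| 100% | 800 | 2.77% | 500 | 3.51% |
| 90% | 720 | 2.92% | 450 | 3.70% |
| 70% | 560 | 3.31% | 350 | 4.19% |
| 50% | 400 | 3.92% | 250 | 4.96% |

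At s = 50% the loss against the 100% row is 3.92 − 2.77 = 1.15 points and 4.96 − 3.51 = 1.45 points.

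**Step 4: vary the rate, with no loss of patients.** Table 5 shows a single p. The formula is symmetric about 50%.

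| p | n = 800 | n = 500 |
|---|---|---|
| 20% | 2.77% | 3.51% |
| 50% | 3.46% | 4.38% |
| 80% | 2.77% | 3.51% |
| 90% | 2.08% | 2.63% |

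The widest case is p = 50%. Rates between 20% and 80% give wider intervals than at 20%; rates above 80% give narrower ones.

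**The case against.** The best defence is that 800 and 500 are planning scenarios for evaluable patients, already reduced from 1000, and that the abstract speaks of allowing for non-evaluable data loss. If 800 and 500 patients did meet every condition, the stated half-widths would stand. That much is correct, and it is why the figures are best called best-case values. It does not remove the mismatch, because Section 9.5 itself defines evaluable as having data on at least one effectiveness endpoint, not as having two tests after initiation.

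The low stakes also stand as an argument. The study tests no hypothesis, the endpoint is secondary, the primary safety objective has its own calculation in Table 4, and at a 90% share the change is only 0.15 points (2.92 − 2.77) and 0.19 points (3.70 − 3.51).

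The two-test restriction is stated openly and consistently, and two negatives in a row cannot be observed on fewer than two tests. Deaths are captured by the separate progression-or-death endpoint. That the restriction leaves out patients who are discharged or die before a second test is therefore a matter for supplementary reporting, not an error in the plan.

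**Conclusion.** The point holds as a mismatch between the sizing text and the endpoint definition. The half-widths of 2.77% and 3.50% are the best the endpoint can have at p = 20% under the planned numbers. With an assumed 90% to 50% of patients meeting the two unnamed conditions, they become 2.92% to 3.92% and 3.70% to 4.96%. The direction at fixed p is certain; the size depends on a share that the protocol does not give.

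Three stronger readings are tempting, and the documents do not support them.

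- *The figures are miscalculated.* They follow from the stated formula and inputs, except that 3.506% was cut to 3.50%.
- *A 20% rate contradicts the planned Kaplan-Meier median for the same event.* Section 9.7.3.2 plans to report a median and does not say it will be reached. Section 9.3.8 censors patients without the event at the end of observation, which includes discharge, so a crude 20% can coexist with an estimable median. For example, with constant hazards and censoring at four times the event hazard, the crude proportion is 1/(1 + 4) = 20%. The survival curve still reaches 50% when exp(−5 × 0.693) = 3.1% remain at risk, about 25 of 800.
- *The true interval must be far wider than stated.* Combining a 70% share with p = 50% gives 4.14% and 5.24%, but neither value is in the protocol, and a rate above 80% would work in the other direction.

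**What to change.** Restate Section 9.5 and Table 5 for EAS1 and EAS patients with at least two tests after initiation. State the assumed share who meet the two-test and 5-day conditions, or show a range such as 50% to 90%. Give half-widths at p = 20% and at the conservative p = 50%, and print 3.51% in place of 3.50%. Carry the same figures into the abstract.

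Optionally, report the clearance proportion over all EAS1 and EAS patients as well, counting those with fewer than two tests as not shown to convert, beside the figure for those tested at least twice.

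The cost is a slightly less favourable stated precision and, if the option is taken, one extra output row. No additional patients or data are needed.
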